Monitoring and blunting coping tendencies have also been shown to influence the extent to which individuals prefer to pay close attention to their wellbeing or avoid thinking about it (Murris & Van Zuuren, 1992; Miller, 1987). Those who employ monitoring to cope with health problems will actively seek out health information, whereas those who employ blunting will adopt distraction strategies in order to actively avoid health information (Miller, 1995). This information seeking preference is important as evidence suggests that acquisition of health information can lead to increased health anxiety in individuals who exhibit monitoring coping preferences (Miller, 1995). In the case of menopausal symptom monitoring, women's attention is drawn to information about their menopausal wellbeing, which may be anxiety provoking. Therefore, this measure will help us understand whether symptom monitoring is more or less effective as an intervention for women, depending on their health information-seeking preferences.

It is important to establish for whom symptom monitoring might be most helpful, or conversely taxing or even harmful should it challenge a dispositional tendency to avoid focusing on wellbeing. Indeed, coping style and neuroticism have both been associated with increased health anxiety following the procurement of health information (Lagoe & Atkin, 2015; Miller, 1987). Therefore, health anxiety will also be measured during this research to explore whether symptom monitoring influences it, and whether this effect is related to neuroticism or coping preferences.

A third objective is to investigate whether participants attribute the act of monitoring to any perceived improvements, or whether participants attribute other elements of research participation to their improved health (i.e. increased menopausal awareness), or whether participants do not perceive any improvements whatsoever. Studies which have included symptom monitoring as a control intervention often speculate that involvement in research is responsible for the positive outcomes found in the control group, rather than symptom monitoring in itself (Borud et al., 2010). However, these studies rarely provide data on this assumption. Therefore, the present study aims to establish whether participation in menopausal research per se improves wellbeing, regardless of what that participation entails.

Summary of objectives:

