- **Perceived effects of research engagement:** Three items (to be completed after the 2-week research period) will assess whether research participation has led to any perceived improvements in emotional and physical well-being: "Since your engagement in this research, what changes have you noticed in your physical or emotional well-being? "If you have experienced any changes, why do you think these changes occurred?" and "what impact has participating in this research had on your physical or emotional well-being?". These items will allow for more specific assumptions to be made about whether the use of symptom monitoring in research is attributed to perceived improvements, and whether researchers employing symptom monitoring as a control intervention should be wary of this occurrence. **To view how the research engagement questions will be presented on the follow-up**

FACULTY OF LIFE SCIENCES AND EDUCATION
FACULTY ETHICS SUB GROUP APPLICATION FORM

survey, see Appendix 3, page 8.

- **Covid-19 experience question:** A final qualitative item will also be used to assess participants' experiences in dealing with the menopause during the Covid-19 pandemic: "Experiencing the menopause during the Covid-19 pandemic might be especially challenging for some women. Please use this space to tell us more about this experience if you wish. E.g., did you feel able to consult a GP when you needed to? Did any changes due to work restrictions or changes in home circumstances feel different because of the menopause? Did the menopause make you feel more or less able to cope?". This item was included in order to gain perspective on the wider context in which this research is taking place, in order to understand how the 2020 pandemic has impacted research findings. **To view the Covid-19 experience question as it will be presented on the follow-up survey, see Appendix 3, page 8.**

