13. DATA COLLECTION TOOLS

Have you tested the data collection tool(s) for face validity? Where **more than one tool** is being utilised please fill in the table.

YES, NO

NA (ALL tools are already validated)

Title of DCT	Validated by you? (Y / N / NA - already validated)	Is permission necessary?	Do you have permission? (Supply permission separately)
Demographics and medical history (to be assessed at baseline only).	Y	NA	NA
Miller Behavioural Style Scale (MBSS; to be assessed at baseline only).	NA	Y	Y (see Appendix 11, page 1)

FACULTY OF LIFE SCIENCES AND EDUCATION
FACULTY ETHICS SUB GROUP APPLICATION FORM

The neuroticism scale (10 items; $\alpha = .86$) compiled from the International Personality Item Pool (to be assessed at baseline only).	NA	N	NA
General help seeking questionnaire (GHSQ; to be assessed at baseline and follow-up).	NA	Y	Y (see Appendix 11, page 3)
Health anxiety subscale adapted from The Health Orientation Scale (HOS; to be assessed at baseline and follow-up).	NA	N	NA
Patient-doctor communication will be assessed using the Willingness to Communicate about Health Measure (WTCH; to be assessed at baseline and follow-up).	NA	Y	Y (See Appendix 11, page 4)
The Decision Self-Efficacy Scale (to be assessed at baseline and follow-up).	NA	N	NA
The General Self Efficacy Scale (GSE; to be assessed at baseline and follow-up).	NA	NA	NA
Health Consciousness subscale adapted from The Health Orientation Scale (HOS; to be assessed at baseline and follow-up).	NA	N	NA
Two qualitative items (to be assessed at 2 weeks only) will assess whether research participation has led to improvements in	Y	NA	NA

FACULTY OF LIFE SCIENCES AND EDUCATION
FACULTY ETHICS SUB GROUP APPLICATION FORM

emotional and physical well-being: "Since your engagement in this research, what changes have you noticed in your physical or emotional well-being? "If you have experienced any changes, why do you think these changes occurred?"			
Daily record keeping form (DRK). For participants in the intervention group, they will continually fill out the DRK each day throughout the 2-week research period- whereas the control group will complete this form at baseline and at 2 weeks only.	NA	Y	Y (see Appendix 11, page 5)

PART B

N.B. All questions should be addressed (e.g. provide an answer or state why not applicable).

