22. DATA ANALYSIS / STATISTICS

Please describe the arrangements for analysing your data (qualitative and quantitative). Where appropriate discuss what data/statistical analysis will be completed. Where used, please remember to discuss sample size and how the sample size was decided upon.

2 x 2 mixed between-within ANOVA:

The main analysis will include a 2x2 mixed between-within ANOVA to assess differences in symptoms among the symptom monitoring and control groups before and after the 2-week research period. The between-subjects component will encompass the differences in symptoms between the control and intervention groups; the within-subjects variable refers to differences in symptoms before and after the 2-week study period. It is expected that after 2 weeks of symptom monitoring the intervention group will exhibit a greater reduction in symptoms in comparison to the control group (i.e., a significant group x time interaction). As discussed, a power analysis was calculated to identify the minimum sample size needed to detect moderate effects, resulting in the decision to recruit 78 participants, with 39 participants being randomised into each group.

Regressions:

Multiple regressions will explore whether help-seeking intentions as continuous variables as predicted by symptom monitoring group (dummy coded), self-efficacy in patient-doctor communication, self-efficacy in shared decision making, health and symptom awareness, and self-efficacy in goal orientated behaviour, health anxiety, and menopausal symptom changes.

Logistic regressions will establish whether control or intervention group membership (as measured as a dichotomous “Invention/Control” variable) is predicted by health anxiety, variances in emotions and symptoms, help-seeking intentions, self-efficacy in patient-doctor communication, self-efficacy in shared decision making, health and symptom awareness, and self-efficacy in goal orientated behaviour.

Correlations:

FACULTY OF LIFE SCIENCES AND EDUCATION
FACULTY ETHICS SUB GROUP APPLICATION FORM

Correlations will also be computed to assess for associations between certain variables. For example, higher neuroticism X higher negative emotions.

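### The third objective turns partly on whether women perceived any improvement, but no follow-up item asks whether well-being became better, stayed the same or became worse

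*Combined protocol and SAP*

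**What the plan says.** Section 7 sets out the objective in three parts. It opens: "A third objective is to investigate whether participants attribute the act of monitoring to any perceived improvements". The second part is the alternative that women credit some other aspect of being in the study. The third part is "whether participants do not perceive any improvements whatsoever". The objective is one of three bullets in the summary of objectives.

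Section 9 (Perceived effects of research engagement) and the follow-up survey in Appendix 3 give the measures, all free text:

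- Item 8: "Since your engagement in this research, what changes have you noticed in your physical or emotional well-being".
- Item 8b asks why the changes occurred, if there were any.
- Item 8c: "what impact has participating in this research had on your physical or emotional well-being".

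Section 9 says that these items assess perceived improvements. Section 22, whose prompt covers qualitative as well as quantitative data, describes an ANOVA, multiple and logistic regressions and correlations. It does not mention these items.

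On completeness, section 10 excludes from analysis women who do not complete all study materials, and section 27 makes the voucher depend on full completion of the follow-up measures.

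**The concern.** To report on this objective, the analyst must first know whether a woman thinks she improved. Only then does it make sense to ask what she credits. The items go straight to changes, causes and impact without that first step. A reply such as *my sleep and my mood* to item 8 names areas of change but not whether they improved or worsened. A blank could mean no change, no wish to answer or an unfinished form.

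The possible loss is at the boundary between improvement and no improvement. If that boundary is blurred, so is any statement about how many of those who improved credited monitoring. Once the survey has closed, the missing direction cannot be reliably recovered.

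**Working it through.** The plan states no figure for this objective, so there is nothing to reproduce. The check sets what the objective needs against what the survey asks.

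**Step 1. What each item records (Appendix 3)**

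| Item | Change or impact taken as given? | Direction asked? | Monitoring separated from other parts of taking part? |
|---|---|---|---|
| 8 | Yes (change) | No | No |
| 8b | No, conditional on change | No | No; one open reason for all changes |
| 8c | Yes (impact) | No | No; asks about the research as a whole |

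No item asks for direction. A woman may volunteer it, or may write that nothing changed, but nothing makes sure that she does.

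**Step 2. How a blank would be read**

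Item 7b, just before, tells women to enter n/a where it does not apply. Item 9, just after, is worded as optional. Items 8 to 8c carry neither instruction. Under sections 10 and 27 a blank could count either as no change or as an incomplete form. If it counts as incomplete, the women most likely to be lost are those who noticed nothing. Whether the live survey forces an answer cannot be seen from the documents.

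**Step 3. Whether another measure fills the gap**

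The DRK gives scored symptoms and emotions over the past 24 hours at baseline and follow-up. A change in that score is measured change. The objective concerns perceived change, so the DRK does not replace a direct question.

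**Step 4. What a closed item could deliver at this sample size**

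Inputs from section 10: 39 randomised per arm; 26 per arm required by the power analysis; about 33% attrition from earlier two-week studies. Check: 39 × (1 − 0.33) = 26.1. The share answering better is not given in the documents. I take 30% as an assumption, with 10% and 50% as the range.

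Wilson 95% intervals for the share in one arm:

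| Assumed share | 26 per arm | 39 per arm |
|---|---|---|
| about 10% | 3/26: 4% to 29% | 4/39: 4% to 24% |
| about 30% | 8/26: 17% to 50% | 12/39: 19% to 46% |
| about 50% | 13/26: 32% to 68% | 20/39: 36% to 66% |

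Approximate 95% half-width for a difference between arms, with the same share p in both: 1.96 × √(2p(1 − p)/n).

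- p = 0.3, n = 26: 1.96 × √(0.42/26) = 1.96 × 0.127 = 0.25
- p = 0.3, n = 39: 1.96 × √(0.42/39) = 1.96 × 0.104 = 0.20
- p = 0.1, n = 26: 1.96 × √(0.18/26) = 1.96 × 0.083 = 0.16
- p = 0.5, n = 26: 1.96 × √(0.50/26) = 1.96 × 0.139 = 0.27

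The item would therefore give a rough description by arm, not a precise comparison. It would, however, record direction and no change for every woman who answers it.

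**The case against.** The strongest reply is that these are qualitative items serving an exploratory aim. The documents call them qualitative and promise no proportion, no sorting of each woman into one class and no comparison between arms. Open text can be coded for direction, cause and absence of change. Item 8b expressly allows for no change. On this view, all that is missing is a coding frame, which is a matter of detail.

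Much of that stands. Three stronger readings are tempting, and the documents do not support them:

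- *That the items cannot yield the distinctions in the objective.* They can, wherever a woman writes enough to be coded.
- *That the wording steers answers towards benefit.* Items 8 and 8c presume that something happened, but change and impact are neutral between better and worse.
- *That the entry in section 13, "Two qualitative items (to be assessed at 2 weeks only) will assess whether research participation has led to improvements in", shows that the measure is unsettled.* Sections 8 and 9 and Appendix 3 agree on three items. The count in section 13 is a clerical slip and says nothing about whether attribution can be measured.

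The objection does not answer one point. A coding frame can sort only what was written. Where the reply is silent on direction, or blank, no later coding supplies it.

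**Conclusion.** The point holds as a cheap improvement to the survey. The objective includes separating perceived improvement from none, yet two of the three items presume change or impact and none asks for direction. Direction and the absence of improvement are therefore not reliably captured. The effect is confined to one of three summary objectives; the main ANOVA and the outcome scales are not affected.

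How many replies would prove unclassifiable cannot be estimated from the documents, and I attach no figure to it. The conclusion rests on the survey wording in Appendix 3 and on the completion rules in sections 10 and 27. If the live survey forces an answer to item 8, the ambiguity about blanks largely goes, but the missing direction remains.

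A reader might also want attribution to monitoring compared between arms. The design does not support that for daily monitoring, because controls complete the DRK only at baseline and follow-up (section 8).

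**What to change.** **Survey.** In the follow-up survey, in both arms, after the DRK (item 7) and before item 8, add one closed item with two rows: *Since joining the study, is your physical / emotional well-being better, no different or worse?* Leave open items 8, 8b and 8c as they are, after it. If a closed attribution question is wanted, put it after the free text so that its options do not prime the open answers, and ask it separately for each row rated better.

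**Reporting.** Add to section 22:

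- the distribution of better, no different and worse for each row by arm, with a 95% confidence interval for the difference in better, described as unblinded self-report;
- attribution to daily monitoring as a description in the intervention arm only.

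**Cost.** One or two tick-box items and one table. The new item may prompt women slightly to think about change before they answer item 8. It cannot affect the outcome scales, which have already been answered by then.

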10. PARTICIPANTS

Discuss the number of participants required, from where the participants will be recruited, and the exclusion and inclusion criteria. Please include power calculations where applicable.

Participants will be recruited using a research poster which will be presented both on JISC's research participant finder service: www.callforparticipants.com and social media sites: Facebook, Instagram and Twitter. **See Appendix 7 to view the recruitment poster as presented on www.callforparticipants.com, and shared on social media sites.** All participants who meet eligibility criteria and research terms will be provided with a £20 Amazon voucher after completing the study to thank them for their time.

Participants will be randomised using online resource: www.randomizer.org. Randomizer is a free resource for researchers in need of a quick way to generate random numbers or assign participants to experimental conditions. This site can be used for a variety of purposes, including psychology experiments, medical trials, and survey research. Randomizer works by generating a series of random unique numbers, therefore to allocate participants into the intervention group 1 set of 39 random numbers were generated using values ranging from 1-78. These figures were chosen following insights from the power analysis (see below).

Random number generation will be used to allocate participants into groups. Participants will be assigned a number when they join the study by submitting the baseline survey- this number will reflect the order in which they joined the study i.e. the first person to join will be assigned as number 1, the second will be assigned as number 2. This number will determine whether they are in the control or intervention group by using random numbers generated by randomizer.com. Randomizer works by generating a series of random unique numbers, therefore, to allocate participants into the intervention group, 1 set of 39 random numbers will be generated using values ranging from 1-78. If the participant's assigned number matches one of the 39 random numbers generated, they will be allocated into the intervention group. If their number is not on the random number list, they will be allocated into the control group.

Inclusion criteria: this study will involve adult females, who report at least 2 hot flushes per day, with self-reported peri- or post-menopausal status. Women taking menopause-specific treatments (e.g. HRT or anti-depressants) are included in this study provided they reach the criteria for hot flushes and are otherwise healthy.

Exclusion criteria: participants will be screened out of the survey if they answer no to the following questions, which will be presented before the information sheet, consent form and main survey: "Are you over the age of 18?", "Are you experiencing at least 2 hot flushes per day?", and "Are you experiencing either perimenopause or menopause?"

Additionally, care will be taken to identify and exclude outliers from analyses, especially when considering the data of those who say they have been diagnosed with chronic or severe conditions with symptoms overlapping with menopausal symptoms, including chronic fatigue syndrome, fibromyalgia, cancer, heart

**FACULTY OF LIFE SCIENCES AND EDUCATION
FACULTY ETHICS SUB GROUP APPLICATION FORM**

disease, thyroid disorders, depression and other mental illnesses. As the research team is not medically trained, we are not able to ascertain definitively if women do have any medical conditions. However, women will be informed in the information sheet that they should not participate if they have these conditions for the reason stated above, and those who report such conditions in the demographic and medical history will be statistically assessed with caution using univariate and multivariate analyses, and data from these individuals will be excluded where necessary. Participants who do not complete all study materials or comply fully with the experimental protocol will also be excluded from analyses. Participants who report demographic characteristics that have been related to poorer health will also be assessed as covariates. Differences in symptoms between groups according to employment status, living status and relationship status will be analysed to understand variances in health between these groups. This is because unemployed, or single, or individuals who live alone are more likely to report poorer health than others.

Power analysis:

An a priori power analysis was conducted using G*Power 3 (Faul, Erdfelder, Lang, & Buchner, 2007) to test the difference between two independent group means (accounting for special, main effects, and interactions) using a two-tailed test, a medium effect size ($d = .40$) and an alpha of .05. Results suggested that a total sample of 52 participants with two equal sized groups of 26 was required to achieve a power of .80.

Medium effect sizes were estimated based on Cohen's (1962) conventional values because these values were derived from studies specific to psychological research (Aguinis, & Harden, 2009). Furthermore, medium effect estimates, rather than small estimates, were used for this research because this study is exploratory and small effects on symptom frequency might not be noticeable to participants. Small effects might imply that symptom monitoring as an intervention to help reduce menopausal symptoms may lack meaningful benefit.

Hoerger (2010) found evidence that at least 10% of participants will drop out of internet mediated research and such studies have high attrition rates. Furthermore, several studies have provided data on attrition rates of studies which employ a 2-week intervention period. Lancastle and Boivin's (2008) feasibility study aimed to establish whether a brief coping intervention (positive reappraisal coping intervention; PRCI) was acceptable and practical when evaluated in the context of a randomised trial. Of the 84 women who agreed to participate in the study 55 (65.5%) completed all measures, suggesting an attrition rate of 34.5%. Moreover, Lancastle's (2006) study also evaluated the PRCI alongside a positive mood inductive intervention, and a daily monitoring control group; this research reported a 31% attrition rate.

Therefore, taking into account average attrition rates from internet mediated research (10%), as well as studies which have utilised a 2-week intervention period (33%), it was decided that the proposed study will use a total sample of 78 participants with two equal groups of 39.

11. HAVE NATIONALLY APPROVED / REGULATORY BODY GUIDELINES BEEN FOLLOWED IN PREPARING THIS PROTOCOL?

(E.g. Association of the British Pharmaceutical Industry Guidelines (1983), Royal College of Physicians Guidelines, The Declaration of Helsinki, British Psychological Society guidelines, BERA, etc.). If so, please specify.

- Faculty of Life Sciences and Education Ethics Committee
- GDPR regulations (2018) and the Data Protection Act (2018)
- USW postgraduate researchers (PGR) code of practice

FACULTY OF LIFE SCIENCES AND EDUCATION
FACULTY ETHICS SUB GROUP APPLICATION FORM

- British Psychology Society Code of Ethics for Research with Human Participants

12. HAVE POTENTIAL PARTICIPANTS BEEN INVOLVED IN, PLEASE INDICATE. IF NO, PLEASE INDICATE WHY.

	YES
